4. OBJECTIVES

The eligible study period is expected to be from 01 September until 30 November 2017.

4.1. Primary objectives

- To estimate the weekly and cumulative incidence rates of AEIs within 7 days following vaccination with any seasonal influenza vaccine using card-based ADR reporting system. Data will be presented overall, by brand (Fluarix Tetra vs. others), by age strata, and UK CMO-specified risk groups status (at risk/not at risk)

4.2. Secondary objectives

- To estimate the weekly and cumulative incidence rates of AEIs within 7 days following vaccination with any seasonal influenza vaccines using the card-based ADR reporting system as well as medically attended AEIs. Data will be presented overall, by brand (Fluarix Tetra vs. others), by age strata, and UK CMO-specified risk groups status (at risk/not at risk)

4.3. Tertiary objectives

- To estimate on a weekly basis the vaccine uptake among the subjects registered in the enrolled GP practices, by age strata (6 months to 5 years; 6 to 12 years; 13 to 17 years; \geq 18-65 years; $>$ 65 years) and UK CMO-specified risk groups
- To assess the completeness of vaccination data in the EHR
- To assess the timeliness of availability of vaccination data in the EHR
- To evaluate the return rate of ADR cards
- To assess the timeliness of AEI reports in the EHR from medically attended AEIs and from the card-based ADR reporting system
- To assess the timeliness of generating weekly reports

5. ENDPOINTS

5.1. Primary endpoints

- Occurrence of AEIs ([Annex 2](#)) within 7 days post vaccination reported using a card-based ADR reporting system overall, by age strata (6 months to 5 years; 6 to 12 years; 13 to 17 years; \geq 18-65 years; $>$ 65 years) and UK CMO-specified risk groups status (at risk/not at risk), each week and cumulatively, overall and by vaccine brand (Fluarix Tetra vs. others). AEIs will be presented by system organ categories

5.2. Secondary endpoints

- Occurrence of AEIs within 7 days post vaccination reported using data entered in EHR (i.e., AEIs derived from a card-based ADR reporting system and medically attended AEIs) overall, by age strata (6 months to 5 years; 6 to 12 years; 13 to 17 years; \geq 18-65 years; $>$ 65 years) and UK CMO-specified risk groups status (at risk/not at risk), each week and cumulatively, overall and by vaccine brand (Fluarix Tetra vs. others). AEIs will be presented by system organ categories

5.3. Tertiary endpoints

- Seasonal influenza vaccination status among the subjects registered in the enrolled GP practices, overall, by vaccine brand, by age strata (6 months to 5 years; 6 to 12 years; 13 to 17 years; \geq 18-65 years; $>$ 65 years) and UK CMO-specified risk groups and date of vaccine administration collected in the EHR system
- Level of missing data related to vaccination information (date of event, vaccine brand, vaccine batch)
- Lag time between date of vaccine administration and date at which vaccination record is encoded in the EHR system
- Return of ADR cards
- Time interval between AEI onset date and recording in the EHR by source (medically attended vs via ADR cards)
- Time interval between the date data extraction and date at which the weekly report is generated

6. ANALYSIS SETS

The following cohorts will be evaluated.

6.1. Total registered population

The Total registered population will include all subjects registered in EHR at any time point during the study vaccination period in the 10 enrolled GP practices who had not opted-out of data sharing.

Note that subjects may have left or joined the GP practices during the study period.

6.2. Total eligible registered population

The Total eligible registered population will include all subjects from the Total registered population

- who have a valid NHS number recorded in EHR
- with date of birth recorded in EHR
- with gender recorded in EHR

6.3. Weekly vaccinated cohorts

The Weekly vaccinated cohorts (for each ISO Week 35 to 48) will include all subjects from the Total eligible registered population

- who are vaccinated with a seasonal influenza vaccine during the week of interest
- who are registered in EHR during the safety follow-up period (from vaccination up to 7 days post vaccination)

Refer to [Annex 4](#) for details of the ISO weeks.

For example, the Weekly vaccinated cohort Week 40 will include all subjects from the Total eligible registered population:

- who are vaccinated with a seasonal influenza vaccine during Week 40
- who are registered in EHR during the safety follow-up period (from vaccination up to 7 days post vaccination)

6.4. Cumulative vaccinated cohorts

The Cumulative vaccinated cohorts (for each ISO Week 35 to 48, denoted as Weeks 35-35 to Weeks 35-48) will include all subjects from the Total eligible registered population

- who are vaccinated with a seasonal influenza vaccine at any point from study start up (i.e. 01SEP2017) up to the end of the week of interest (i.e. cumulatively since the beginning of the study)
- who are registered in EHR during the safety follow-up period (from vaccination up to 7 days post vaccination)

For example, the Cumulative vaccinated cohort Weeks 35-40 will include all subjects from the Total eligible registered population:

- who are vaccinated with a seasonal influenza vaccine at any point from study start up (i.e. 01SEP2017) up to the end of Week 40 (i.e. cumulatively since the beginning of the study)
- who are registered in EHR during the safety follow-up period (from vaccination up to 7 days post vaccination)

7. STATISTICAL ANALYSES FOR THE FINAL ANALYSIS AFTER STUDY COMPLETION

All data processing and statistical analysis will be performed within the secure IT environment of the Clinical Informatics Research Group, at the University of Surrey. R and SAS will be used for the statistical analyses.

Note that statistical methods and data derivation rules are described in [Annex 1](#) and will not be repeated below.

7.1. Analysis of demographics/baseline characteristics

Characteristics of the enrolled GP practices (Clinical Commissioning Group (i.e. the administrative health division used in England), location (North/South/ London/Midlands and East), Urban/Rural, mean IMD, number of registered subjects (rounded to the nearest 1000 to avoid the identification of the practices) will be tabulated.

The number of subjects in the Total registered population as well as the number excluded from the Total eligible registered population and from the Cumulative vaccinated cohorts will be tabulated, with reasons for exclusion

Demographic characteristics will be summarized for the 2012 Census population, the Total eligible registered population and the Cumulative vaccinated cohorts using descriptive statistics:

- Frequency tables will be generated for categorical variables such as gender
- Mean, median, standard deviation, maximum and minimum will be provided for continuous data such as age.

7.2. Analysis of vaccine exposure

The percentage of subjects vaccinated with a seasonal influenza vaccine during the study vaccination period will be tabulated by Vaccine, Age and UK CMO-specified risk group for the Total eligible registered population as follows:

- The denominator will be the number of subjects in the Total eligible registered population
- The numerator will be the number of subjects from the denominator who were vaccinated with a seasonal influenza vaccine during the study vaccination period

Cumulative percentage of subjects vaccinated with a seasonal influenza vaccine will be graphically displayed by ISO week for the Total eligible registered population.

The number of vaccinated subjects will be tabulated, for the Cumulative vaccinated cohort Weeks 35-48, by GP practice and:

- Vaccine batch number for the group Vaccinated (GSK's Fluarix Tetra)
- Vaccine brand code (A, B, C,...) for the group Vaccinated (Non-GSK) in order to not disclose the detailed information from other manufacturers.

In addition, the list of GSK's Fluarix Tetra vaccine batch numbers administered during the study vaccination period will be provided by Region and Week.

7.3. Analysis of safety

The analyses will be descriptive and will be presented by Vaccine group.

7.3.1. ADR compliance

The percentage of subjects who received and who returned the ADR card will be tabulated by Vaccine group for the Cumulative vaccinated cohort Weeks 35-48.

7.3.2. Analyses of primary objectives

The weekly incidence rate (per 100 subjects) of any AEIs within 7 days* post-vaccination period reported via ADR card will be estimated by Vaccine group as follows in the Weekly vaccinated cohorts restricted to subjects who received the ADR card:

- The denominator will be the number of subjects in the Weekly vaccinated cohort for the week of interest who received the ADR card
- The numerator will be the number of subjects from the denominator who reported any AEIs on the ADR card within 7 days following vaccination with the seasonal influenza vaccine

**Day of vaccination plus the following 7 days*

The cumulative incidence rate (per 100 subjects) of any AEIs within 7 days post-vaccination period reported via ADR card will be estimated by Vaccine group as follows in the Cumulative vaccinated cohorts restricted to subjects who received the ADR card:

- The denominator will be the number of subjects in the Cumulative vaccinated cohort up to the week of interest who received the ADR card
- The numerator will be the number of subjects from the denominator who reported any AEIs on the ADR card within 7 days following vaccination with the seasonal influenza vaccine

Similarly, weekly and cumulative incidence rates will be estimated for the following AEIs within 7 days post-vaccination period reported via ADR card:

- Fever/pyrexia
- Fever $>38.5^{\circ}\text{C}$ and $>39.5^{\circ}\text{C}$ (with a temperature measurement recorded in EHR; independent of route of measurement)
- Local symptoms (i.e. local erythema)
- Any and each general non-specific symptom: drowsiness, fatigue, headache, irritability and malaise
- Any and each respiratory AE: conjunctivitis, coryza, cough, epistaxis, hoarseness, nasal congestion, oropharyngeal pain, rhinorrhoea, wheezing
- Any and each gastrointestinal AE: decreased appetite, diarrhea, nausea, vomiting
- Any and each sensitivity/anaphylaxis AE: anaphylactic reactions, facial oedema, hypersensitivity reactions
- Rash
- Any and each musculoskeletal AE: arthropathy, muscle aches / myalgia
- Any and each neurological AE: Bell's palsy, Guillain-Barre syndrome, peripheral tremor, seizure / febrile convulsions

Similarly, weekly and cumulative incidence rates of any SAEs within 7 days post-vaccination period reported via ADR card will also be generated.

In addition, weekly and cumulative incidence rates of any AEIs, each AEIs category (i.e. fever/pyrexia, local symptoms, any general non-specific symptom, any respiratory, any gastrointestinal, any sensitivity/anaphylaxis, rash, any musculoskeletal and any neurological AEs) and SAEs within 7 days post-vaccination period reported via ADR card will also be generated by Age group (6 months to 5 years; 6 to 12 years; 13 to 17 years; 18-65 years; >65 years) and by UK CMO-specified risk status (at risk, not at risk).

95% confidence interval (CI) adjusted for clustering effect of GP practices will be computed on all estimated incidence rates (Clopper-Pearson exact CI modified for cluster data as described in [Annex 1](#)).

The design effects and the intra-cluster correlation coefficients will also be estimated as described in [Annex 1](#) for the estimated cumulative incidence rates of AEIs reported on the ADR card within the 7 days post-vaccination period for the Cumulative vaccinated cohort Weeks 35-48 restricted to subjects who received the ADR card.

7.3.3. **Analyses of secondary objectives**

All analyses described for the primary objectives (refer to Section [7.3.2](#)) will also be generated by Vaccine group for all subjects included in the Weekly vaccinated cohorts and the Cumulative vaccinated cohorts (i.e. whether or not they received the ADR card).

For the weekly incidence rates (per 100 subjects):

- The denominator will be the number of subjects in the Weekly vaccinated cohort for the week of interest
- The numerator will be the number of subjects from the denominator who reported the specified AEI within 7 days following vaccination with the seasonal influenza vaccine using data entered in the EHR (i.e. AEIs derived from ADR card and medically attended AEIs)

For the cumulative incidence rates (per 100 subjects):

- The denominator will be the number of subjects in the Cumulative vaccinated cohort up to the week of interest
- The numerator will be the number of subjects from the denominator who reported the specified AEI within 7 days following vaccination with the seasonal influenza vaccine using data entered in the EHR (i.e. AEIs derived from ADR card and medically attended AEIs)

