All data processing and analysis in the study will be conducted within the secure IT environment of the Clinical Informatics Research Group, at the University of Surrey. The information security policies and procedures of the Research Group have been approved by the NHS Digital as meeting Information Governance Toolkit (IGT) standards^{xii}.

The system is continuously being updated and modernized in respect of information processing, security and governance processes. The data are automatically extracted from the network of GP practices using a Simple Object Access Protocol (SOAP) web service, on a weekly basis. Data are uploaded to a secure Microsoft SQL server, and processed into aggregated tables; these are then linked to a pre-defined report structure using business intelligence software (Tableau Software, Inc. Seattle, WA, www.tableau.com), to produce a weekly surveillance report in a timely manner.

Using the EHR system, routine data as well as the content of encoded ADR cards will be extracted using methods that Surrey developed and deploys to extract RCGP RSC surveillance data. Sensitive coded data and free-text data will not be extracted. Only relevant EHR data for this study (e.g. disease or symptom, vaccination status and brand) coded by the GPs or other health professional will

¹ This is also referred to as “3DES”, which is the commonly used name for the triple data encryption algorithm (TDEA, also written Triple DEA) symmetric-key block cipher.

² RSA stands for Rivest, Shamir and Aldeman who founded RSA Laboratories. They created large numbers with only two prime factors, a core component of the encryption process

be extracted^{xiii}. Large volume of research that has come out of UK primary care is based on coded data^{xiv}. The quality of primary care data are such that the expectation will be able to detect frequent AEIs.^{xv}

GP practices will be required to use the relevant Read code for ADR notifications, when recording data from a returned card (Read Code: PPD - Adverse drug reaction notification).

Relevant coded data will be extracted, however these are limited to the administration regime, AEIs and batch number fields of prescribing data.

The following routinely collected patient data will be extracted for the study:

- Demographic information: age, gender, ethnicity, date of registration.
- Seasonal influenza vaccine information: date of administration, brand and batch number when available

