Mild fever (<38.5°C rectal)			Please include level of temperature, to help us classify the fever
Moderate fever (38.6-39.5°C)	2E3..	2E3..	
High fever (>39.5°C)			
Sensitivity/anaphylaxis			
Hypersensitivity reactions	SN52.	Xa5uf	Allergic reaction
Anaphylactic reactions	SN501	X70vr	Other allergic reactions
Facial oedema	16J5.	Xa0ls	Facial swelling
Rash			
Rash	M130.	X50Ge	
Generalised rash	2I14.	XM07J	
General non-specific symptoms			
Irritability	225A.	225A.	
Drowsiness	1B67.	XM06R	
Fatigue	168..	1682.	
Headache	1B1G.	XM0CV	
Neurological			
Bell's palsy	F310.	F310.	
Peripheral tremor	1B22.	XE0rn	Tremor/shaking
Guillain-Barre Syndrome (GBS)	F3700	F3700	
Seizure/ Febrile convulsions	1B64.	XaDbE	
	1B6B.	XM03I	Seizure/ fits
Musculoskeletal			
Muscle aches/ myalgia	N2410	X75rs	
Arthropathy	N037.	X701f	Joint pain
Local Symptoms			
	SP3y4		
Local erythema	SP3y5	X75ty	Local reaction to vaccine
	SP3y6		
	SP3y7		

If a patient hands back an Orange Card with their symptoms – please code these and include the code 9G4.. (Drug reaction notification).

N.B.: In coding these conditions there is no assumption about causation; this can only come from advanced analytics.

Principal Investigator: [name]

Practice Liaison Officer: PPD

Project title: Post-authorisation passive enhanced safety surveillance of seasonal influenza vaccines: Pilot study in England– Preferred code list

If a patient presents with adverse events post-vaccination (up to 7 days after), please code (ideally as a problem) as any of the following please code them into the patients computerised record

EMA surveillance condition	Read Code (5 Byte)	Read Code (CTV3)	Notes
Respiratory/Miscellaneous			
Conjunctivitis	F4C0.	XE16X	Sticky eyes
Rhinorrhoea	1C83.	XM00h	Runny nose
Nasal congestion	H1y1z	X77Gp	Blocked nose
Epistaxis	R047.	Xa96W	Nose bleed
Coryza	H00..	XE0XI	Common cold
Cough	171..	XM0Ch	
Oropharyngeal pain	1922.	1922.	Sore throat
Hoarseness	1CA2.	1CA2.	Hoarse voice
Wheezing	1737.	XE0qs	
Gastrointestinal			
Decreased appetite	R0300	XM07Y	
Nausea	198..	X75qw	Feeling sick
Vomiting	199..	XE0rA	Being sick
Diarrhoea	19F..	19F2.	
Fever/pyrexia			
Fever	165..	X76DI	
Mild fever (<38.5°C rectal)			Please include level of temperature, to help us classify the fever
Moderate fever (38.6-39.5°C)	2E3..	2E3..	
High fever (>39.5°C)			
Sensitivity/anaphylaxis			
Hypersensitivity reactions	SN52.	Xa5uf	Allergic reaction
Anaphylactic reactions	SN501	X70vr	Other allergic reactions

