Appendix 3 ADR formVersion 1 – May 15th, 2017

CONFIDENTIAL Card unique number: 0000 0000 0000 0

Enhanced safety surveillance of seasonal influenza (flu) vaccine

Study of possible adverse events following immunisation – this surveillance is designed to capture all adverse events following immunisation. Please report if you get any symptoms following your “flu jab” (influenza vaccination).

1. About you – this information is kept confidential and won't leave your practice

About you* we need contact details, please supply a full address so we can link this to your medical record:

First name _____ Surname _____
 Address _____
 Postcode _____ Telephone: _____ Email _____ @ _____
 Signed _____ Date _____ / _____ /2017

*This personal information is only being collected to link any side effects to your record

2. When you were vaccinated / When was the influenza vaccination given

What date were you vaccinated / was the vaccine given _____ / _____ /2017

Where were you vaccinated: At your GP surgery: Yes No If no, say where: _____

3. If you were not the person vaccinated

Information about the person* Male Female Date of Birth _____ / _____ / _____

First name _____ Surname _____

4. Please report any side-effects/conditions in the 7 days after your flu vaccine

Please look at the list of possible vaccine side-effects on the next page – if the person vaccinated has experienced any adverse events – please tick the relevant box and indicate the severity

Please also mark if the symptoms/possible side effects are still persisting

Please return the card in the envelope provided to your GP – please return by post or in person.

Thank you for your help

5. If you had no side effects in the 7 days after vaccination tick and return

I/the person vaccinated has NOT had any side effects or other symptoms following vaccination:

Please return the card in the envelope provided to your GP – please return by post or in person.

Thank you for your help

Formal study name:

Post-authorisation passive enhanced safety surveillance of seasonal influenza vaccines:

Pilot study in England

GSK study abbreviation:

EPI-FLU 046 VS UK

Collaborating Study Sponsors:

University of Surrey, Guildford UK

GlaxoSmithKline Biologicals

Contact:

[name]

Professor of Primary Care and Clinical Informatics

E-mail: PPD

Telephone: +PPD

PPD

Practice Liaison Officer

E-mail: PPD

Telephone: +PPD

Enhanced safety surveillance of seasonal influenza vaccine

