3.3.2. Adverse Drug Reaction card

In order to facilitate the coding of data using a standardised approach, the 10 enrolled GP practices will also distribute an ADR card to their subjects receiving seasonal influenza vaccine or, as appropriate, to their parent or carer.

Subjects will be instructed to record adverse events (refer to [Annex 3](#)) within 7 days following vaccination and to return the card to their GP practice not later than 14 days post-vaccination. Data recorded on these cards will then be recorded by the GP staff into the subject's EHR. The coding will follow a standardised approach to data recording (refer to [Annex 2](#)) and will include a specific code to indicate that the information is derived from those cards.

Of note, the intent will be to issue cards to all vaccinated patients belonging to the enrolled GP practices, however, considering the UK influenza vaccination plan, some vaccinations are expected to occur outside of the GP settings. These are described as opportunistic vaccination, performed by third parties including pharmacists and thus it cannot be excluded that for some patients, ADR cards will not be distributed. These vaccinations will still be encoded in the EHR and those subjects will be included in the study. The adverse events (AEs) will be captured through the routine data collection process (refer to Section 3.3.1).

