13. ANNEX 2 PREFERRED CODE LIST FOR ADVERSE EVENTS OF INTEREST

If a patient presents with adverse events post-vaccination (up to 7 days after), please code (ideally as a problem) as any of the following please code them into their computerised record

EMA surveillance condition	Read Code (5 Byte)	Read Code (CTV3)	Notes
Respiratory/Miscellaneous			
Conjunctivitis	F4C0.	XE16X	
Rhinorrhoea	1CB3.	XMO0h	
Nasal congestion	H1y1z	X77Gp	
Epistaxis	R047.	Xa96W	
Coryza	H00..	XEOX1	
Cough	171..	XMOCh	
Oropharyngeal pain	1922.	1922.	
	1CB3.	1CB3.	
Hoarseness	1CA2.	1CA2.	
Wheezing	1737.	XEOqs	
Gastrointestinal			
Decreased appetite	R0300	XMO7Y	
Nausea	198..	X75qw	
Vomiting	199..	XEOrA	
Diarrhoea	19F..	19F2.	
Fever/pyrexia			
Fever	163..	X76D1	
Mild fever (<38.5°C rectal)			Please include level of
Moderate fever (38.6-39.5°C)	2E3..	2E3..	temperature, to help us classify the fever
High fever (>39.5°C)			
Sensitivity/anaphylaxis			
Hypersensitivity reactions	SN52.	Xa5uf	
Anaphylactic reactions	SN301	X70vr	
Facial oedema	1E15.	Xe0ls	
Rash			
Rash	M130.	X50Ge	
Generalised rash	2114.	XMO7J	
General non-specific symptoms			
Irritability	225A.	225A.	
Drowsiness	1B67.	XMO6R	
Fatigue	168..	1682.	
Neurological			
Bell's palsy	F310.	F310.	
Peripheral tremor	1B22.	XEOrn	
Gullain-Barre Syndrome (GBS)	F3700	F3700	
Seizure/ Febrile convulsions	1B64.	XaDbE	
Headache	1B1G.	XMOCV	
Musculoskeletal			
Muscle aches/ myalgia	N2410	X75rs	
Arthropathy	N037.	X701f	
Local Symptoms			
Local erythema	SP3y4		
	SP3y5		
	SP3y6	X75ty	
	SP3y7		

N.B.: In coding these conditions there is no assumption about causation; this can only come from advanced analytics.

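### SAP 7.3.2 reports anaphylactic reactions as a card-based rate, but the card has no anaphylaxis item and the visible documents do not state where its residual allergy box is coded

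*SAP*

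**What the plan says.** SAP 7.3.2 lists the events that get their own weekly and cumulative rates from the ADR card. One bullet reads "Any and each sensitivity/anaphylaxis AE: anaphylactic reactions, facial oedema, hypersensitivity reactions", so anaphylactic reactions are a separate card-based row.

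The card is printed in Protocol Appendix 3 and again in SAP Annex 3. Both copies offer the same allergy items: allergic reaction (rash), "Other allergic reactions" and facial oedema, followed by free lines for anything else. Anaphylaxis is not named.

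Coding is described in two places:

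- Below the code list in Protocol Appendix 2, practices that receive a completed card are told: "please code these and include the code 9G4.. (Drug reaction notification".
- SAP 3.3.2 refers card coding to SAP Annex 2 and says it "will include a specific code to indicate that the information is derived from those cards".

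For the secondary objective, SAP 7.3.3 counts events "using data entered in the EHR (i.e. AEIs derived from ADR card and medically attended AEIs", so the two sources share a row there.

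**The concern.** A rate labelled anaphylactic reactions will be read as anaphylaxis. The study exists to pick up a change in the frequency or severity of expected reactions, allergic ones included. The Protocol synopsis says the final findings will be discussed beside rates from the RCGP network and from clinical trials. If the row is filled by a catch-all allergy box, that comparison sets unlike things side by side. If the box goes elsewhere, the card can fill the row only through a patient's own words on a free line, and a rate near zero could be taken as reassurance it does not give.

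The extracted codes alone would not settle which case applies. The Protocol states that "Sensitive coded data and free-text data will not be extracted". The card tells patients "please tick the relevant box and indicate the severity", but for this item it prints only a start date and a tick box.

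**Working it through.** No figure in the plan is in dispute, so the check is mainly a comparison of texts.

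**1. The allergy entries side by side**

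| Source | Allergy content |
|---|---|
| SAP 7.3.2 | Rows: anaphylactic reactions; facial oedema; hypersensitivity reactions |
| Card (Protocol Appendix 3, SAP Annex 3) | Boxes: allergic reaction (rash); other allergic reactions; facial oedema; free lines |
| Protocol Appendix 2, both copies | Hypersensitivity SN52. / Xa5uf, note: allergic reaction. Anaphylactic reactions SN501 / X70vr, note: other allergic reactions. Facial oedema, note: facial swelling |
| Protocol Appendix 7 | SN501 described as drug-induced anaphylaxis |
| SAP Annex 2 | A row for "Anaphylactic reactions", with a blank note; the only note on the list concerns temperature |

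The code in this row of SAP Annex 2 reads SN301 in the copy reviewed. That may be a reading artefact, and nothing here rests on it.

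**2. Is the Appendix 2 note a coding key?** The sheet carries 16 lay notes (runny nose, sore throat, joint pain and so on). All 16 correspond to a card item, some with small differences in wording. Staff looking for a code for the residual allergy tick would find one row with those words, the anaphylaxis row. The reading is likely, but nowhere stated.

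**3. The two branches**

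- *The note was the key.* The card row holds residual allergy ticks plus any true anaphylaxis ticked there or written on a free line.
- *The note was not the key.* The card has no dedicated route into the row. SAP 12.2.4 treats subjects with no report as having no event, so the row tends to zero by construction.

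**4. Scale of one entry.** One entry adds 100/n per 100 subjects. The intervals are Clopper-Pearson without the cluster adjustment that the SAP will apply.

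- 5,000 vaccinated (SAP 3.1), all assumed to receive a card: 100/5,000 = 0.02 (95% CI 0.00 to 0.11).
- 1,000 to 10,000 vaccinated (Protocol Table 1): 0.10 down to 0.01.
- Returned cards only (card tables of SAP 7.3.6.1 and 7.3.6.2), at the roughly 50% return reported for the previous pilot: 100/2,500 = 0.04 (0.00 to 0.22); range 100/500 = 0.20 to 100/5,000 = 0.02.

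Safety rates are printed to two decimals (SAP 12.3), so a single entry shows.

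**5. Illustration, with assumed tick rates that are not in the documents.** If 0.05% to 1% of 5,000 card recipients tick the box and every tick is coded SN501, the row expects 5,000 × 0.0005 = 2.5 to 5,000 × 0.01 = 50 subjects with no true case at all. This shows the mechanism and is not an estimate.

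**6. What can still be changed.** SAP 9.1.1 puts each weekly report three weeks after its week. Using the week ends in SAP Annex 4: week 46, 19 November + 21 days = 10 December 2017; week 47, 17 December; week 48, 21 December. The SAP is dated 11 December, so weeks 35 to 46 (12 of 14) were already due. The last cards were due on 30 November + 14 days = 14 December.

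**The case against.** The strongest reply is that the harm depends on an inferred mapping. SAP 3.3.2 points to SAP Annex 2, where the note is blank, and the data-capture flow charts and some pages are not visible, so another instruction may exist. This stands. A reader might infer that the card-based anaphylaxis rate will be inflated, or that the box has no defined code anywhere. The documents support neither as fact.

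A reader might also infer that only the split between the anaphylaxis and hypersensitivity rows is at risk and that the category rates are safe. That assumes the box would otherwise be coded as hypersensitivity, which is not stated. If ticks were left uncoded or coded as rash, the any-sensitivity rate would differ, and an uncoded tick could also alter the any-AEI rate.

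Nor is it right that the sources cannot be told apart. For the same row, the 7.3.3 numerator minus the 7.3.2 numerator gives the subjects with a medically attended entry only; those with both sources stay hidden. The Protocol synopsis also says that events from consultations and from cards will both be listed in the weekly analysis.

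Two further replies carry less weight. The Protocol admits that meaning is inferred from brief coded information without in-depth case definitions, but that general caveat does not tell a reader that this card has no anaphylaxis box. Bell's palsy, Guillain-Barre syndrome and malaise are likewise card rows without a card item. For the first two, however, Appendix 2 sets no broader card wording beside the code, and it has no malaise row.

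**Conclusion.** The point holds as a labelling and traceability gap. The card-based row cannot be interpreted as it stands: under one reading it mixes non-specific ticks with anaphylaxis, and under the other it is close to empty by design. Which reading applies depends on how practices coded the box, which the visible documents do not say.

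The size cannot be derived. The 0.02 per 100 is only the weight of one entry, and it assumes 5,000 vaccinated subjects who all received a card. The effect on the category and any-AEI rates is likewise unknown, because it depends on the alternative destination of the box. Severity is minor: one row, in analyses that SAP 8 declares descriptive throughout.

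**What to change.** 1. Ask the participating practices how the residual allergy box was coded, and state the answer in the SAP. The University team would have to ask, since GSK is blind to practice identities.
2. In the card tables of SAP 7.3.2, 7.3.6.1 and 7.3.6.2, add a footnote that the card has no anaphylaxis item. If the box was coded to SN501 / X70vr, or the coding cannot be confirmed, label the row *anaphylactic or other allergic reaction, card-reported*. If it was coded elsewhere, keep the present label, so that a genuine entry from a free line is not diluted.
3. In SAP 7.3.3 and the EHR table of 7.3.6.1, show SN501 / X70vr entries in two lines, card-derived and medically attended, using the existing card code. Count a subject with both sources once in the total, and recode no entry. Do the same in the weekly reports not yet issued at the SAP date (weeks 47 and 48 on the stated schedule). This fits the synopsis statement about listing both sources.
4. For later seasons, give the box its own stated destination in Protocol Appendix 2 and SAP Annex 2.

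The cost is one query to the practices, one footnote, a possible label change and one extra line, carried into the separate TFL. No new patient data are needed, because 7.3.2 already has to isolate card entries. The relabelling and the split leave every category and any-AEI rate unchanged. The downside is that each source line may rest on very few events.
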